5 STUDY DESIGN

5.1 Overall Design

Design of trial: Observational, case study design

Single or multi-site: Multisite

Methods to minimize bias: The observational study design explicitly incorporates varied context and baseline capabilities between the clinics. This approach could lead to potential selection bias issues. To minimize the potential for this selection bias we have recruited clinics with varied characteristics both private and academic; general rheumatology and lupus clinics to implement the DA from a wide-range of geographical areas.

5.2 Scientific Rationale for Study Design

5.2.1 Rationale for an Observational Study Design

An observational study design was chosen to explicitly incorporate the varied contexts and baseline capabilities between practices.

5.3 End of Study Definition

A patient participant is considered to have completed the study if he or she has completed the baseline visit, and both three and six month telephone interviews. If he/she is selected to participate in the “debriefing”, completion of the study is considered after the above has been completed and the “debriefing” has been completed.

A clinic personnel participant is considered to have completed the study if he or she has completed the formative evaluation (Aim 1); and the standard and targeted decision aid implementation strategies (Aim 2).

If he/she is selected to participate in the semi-structured interview (Aim 3), completion of the study is considered after the interview is completed.

5.4 Inclusion Criteria

Specific Aim 1 Clinic Personnel:

- Clinic personnel involved in the care processes of lupus patients are eligible to participate.

Specific Aim 2 Patients:

- Men and women ≥ 18 years of age
- All races/ethnicities
- Diagnosis of Systemic Lupus Erythematosus

Specific Aim 2 Clinic Personnel:

- Clinic personnel involved in the care processes of lupus patients are eligible to participate.

Specific Aim 3 Clinic Personnel:

- Participating clinical personnel from Specific Aim 1

Specific Aim 3 Patients:

- 2 patient participants randomly chosen from patient participants from Specific Aim 2 from each of the 16 clinic sites.

5.5 Exclusion Criteria

Specific Aim 1 (Clinic Personnel):

- Clinic personnel who are not involved in the care processes of lupus patients.

Specific Aim 2 (Patients):

- No diagnosis of lupus

- Not English or Spanish speaking
- Visually impaired
- Altered mental status

Specific Aim 2 (Clinic Personnel):

- Clinic personnel who are not involved in the care processes of lupus patients.

Specific Aim 3 (Clinic Personnel):

- Clinic personnel who are not involved in Specific Aim 1.

Specific Aim 3 (Patients):

- Patients with lupus who are not involved in Specific Aim 2.

5.6 Lifestyle Considerations

There are no lifestyle considerations applicable to this study.

5.7 Screen Failures

Screen failures are defined as participants (patients) who consent to participate in IDEAL but do not meet eligibility criteria or withdraw consent before reviewing the DA or answering the assessments. Screen failures are also defined as those who meet eligibility criteria but do not consent to participate in the study.

We will collect a minimal set of screen failure information to ensure transparent reporting of screen failure participants, to meet the Consolidated Standards of Reporting Trials (CONSORT) publishing requirements and to respond to queries from regulatory authorities. Minimal information includes demography, screen failure details, and eligibility criteria.

5.8 Strategies for Recruitment and Retention**Key Clinic Personnel Recruitment**

Prior to implementation of the DA, the clinic personnel will be exposed to a brief video animation about the DA content and a link to the DA. We will recruit and conduct semi-structured in-depth interviews via phone with 6-8 key clinic personnel that will address perceived barriers to implementing the decision-aid. The clinic personnel will be identified by the site PI and or/ clinic champion and asked to participate. The site PI and/or the clinic champion will select the clinic personnel to ensure that all areas in each clinic are represented (LPN/RN, Physician, physician-extenders (Physician assistants/nurse practitioners) and Front Desk Staff) (Specific Aim 1).

In addition, all clinic personnel (up to 15 per site), will participate in an online survey (Specific Aim 1) and a regular online survey to assess DA acceptability, feasibility, success etc. (Specific Aim 2). Each site will receive a list of all the clinic personnel emails from their clinics nurse/business manager. The study coordinator will send an email with a link to complete the Qualtrics survey. Reminder emails will be sent to non-responders 1- and 2-weeks after the initial email.

At the conclusion of the study, we will conduct semi-structured in depth interviews via phone with the same 6-8 key clinic personnel, as well as 2 patients selected by the PI to identify implementation lessons learned, and assess anticipated barriers to sustaining the decision-aid after the study is completed (Specific Aim 3).

Semi-structured interviews will be done by phone to reduce participant burden.

Key Clinic Personnel Retention

Clinic personnel will be retained by periodic check-ins (email and phone call) from the research team to ensure the standardized capacity-building activities are being maintained. The clinic champion will be the point of contact to keep staff motivated and consistent while implementing the decision-aid. A refresher training course will be administered to each site every six months and as needed during Aim 2. There will be a portal available (e.g., Google Docs) for all sites to share suggestions and best implementation practices. The standardized and tailored implementation activities (webinars, trainings, coaching, DA reminder in patient intake process, audit and feedback, team huddles/clinic meetings) will keep the clinic staff invested in the value of shared decision making (Specific Aim 2).

Patient Participant Recruitment

We will recruit and enroll up to 3,000 adults (≥ 18 years of age) from 16 geographically diverse sites who have been diagnosed with lupus. Recruitment will include men and women of all races/ethnicities.

Advertisements (flyers) may be placed in clinic rooms and in participating site publications. Flyers will contain information about the study, as well as the study coordinators contact information. Depending on each sites clinic structure other recruitment strategies will be implemented such as decision aid information offered on the patient portal, waiting room TV, or a paper-based version of the decision aid mailed to the patient before the visit detailing the study and time demand. Coordinators will review the inclusion and exclusion criteria prior to approaching potential patient participants during their regular clinic visits about being in the study.

Potential patient participants who agree to participate will be given a non-signature consent form detailing the study purpose and procedures. Participants will also be required to sign a HIPPA document, since some personal health identifiers (PHI) may be obtained (medical record number, conversations between patient and physician). Each patient participant will be informed of the study compensation of \$50 at the baseline visit and \$10 for each follow-up visit that is completed. Once the study has been explained, the non-signature consent form read over by the participant, and the HIPPA document is signed, study procedures will begin.

The study investigators and research team will have meetings weekly to monitor site recruitment and to determine any intervention for poor recruitment. In the event a problem is identified by either study site PI or staff, a teleconference/webinar will be scheduled to review the issue. These teleconferences/webinars will include discussions of overall recruitment status and identified barriers to recruitment experienced by the site with the study team.

Patient Retention

Three and six month follow-up surveys will be conducted by telephone or email (for those who have email access) to reduce patient participant burden. If requested, surveys will be mailed from the Data Coordinating Center (DCC) to patient participants, and will include a pre-stamped return envelope. Reminders will be sent to non-responders 1- and 2-weeks after the initial survey has been completed. Those who have an email will have the option to receive follow-up email reminders. If the reminders are not successful, surveys will be sent to non-responders via U.S. mail.

Patient participants will receive check-in phone calls and appointment reminders from the study coordinator prior to the three and six month follow-up surveys. In the event that a participant is a no-show for their clinic appointment, she/he will be recruited at their next clinic appointment.

The tailored, patient-targeted activities such as pre-visit web-based portal messages with access to the decision aid and information on the study time demand; will retain patients by maintaining a stream of consistent information. Each site will choose a tailored patient-targeted activity to display information about the study via patient portal, clinic poster, waiting room TV/online kiosk, and paper-based versions of the decision aid.

6 STUDY INTERVENTION

6.1 Study Intervention(S) Administration

Specific Aim 1:Clinic Personnel Survey

Clinic personnel will complete a formative evaluation during the first six months of the study, receiving a survey to assess their role in the clinic, clinic culture, as well as their perception on the clinics readiness to implement the DA. This survey will be administered to up to 15 clinic personnel per site at most and will last for 20 minutes. Clinic personnel will receive an email with a link to complete the online Qualtrics survey. Reminder emails will be sent to non-responders 1- and 2-weeks after the initial survey email.

Key Clinic Personnel Interview

The PI/ research coordinator at each site will identify six to eight clinic personnel that are well versed in the flow of the clinic, and will be able to assist in sustaining the intervention once the study is completed. The clinic personnel will view a brief video animation about the value and content of the DA. Semi-structured interviews will be administered to these six clinic personnel over the phone or in person, to explore perspectives on practice needs, and barriers or facilitators to implementing the decision-aid. These interviews will last no more than 60 minutes.

Note: These should not be the study coordinator. Acceptable clinic personnel would be the clinic champion or nurse supervisor.

Before interviews begin, the study team will pilot test the clinic personnel survey and semi-structured interview guides with clinic personnel other than those already chosen for the final interview. The guide will be edited based on feedback from this pilot testing. The study team will take into consideration the following when developing the interview guide for Specific Aim 1:

- Time staff has available for the interview.
 - Most staff, especially physicians or nurses, will not have the entire hour to devote to the interview. The study team will develop a shorter semi-structured interview guide, made up of questions that address key factors for Specific Aim 1 to use in special cases like this.
- Are the interview questions clearly worded? Are any of the questions vague or unclear?
- Interview questions ordered in a way that makes sense? Do any of the questions seem repetitive?

Clinic personnel who agree to participate will be sent the interview questions one-week in advance of the scheduled interview. All clinic personnel (even those who will not be interviewed) will receive an electronic copy of the decision aid and be trained on its use through an educational video. The video will explain what the decision-aid is, as well as suggested methods on how it can be administered to patients in the clinic.

Clinic Personnel surveys will be completed electronically via Qualtrics® (Seattle, WA) and stored for analysis. The semi-structured interviews will be administered over the phone, recorded, and transcribed for analysis in NVivo®.

Specific Aim2: Prior to each site implementing the decision aid; standardized capacity-building activities will be initiated. These activities are as follows:

- Education: A series of 60-minute seminars including all 16 clinics that educates clinic personnel about the decision aid includes its purpose, contents, and supporting evidence.
- Training: A series of webinars, offered 1-2 months after each sites formative evaluation, that describes the clinic-specific findings of the formative evaluation, reviews the implementation strategies available to the clinic (both standardized and tailored), and jointly identifies the preferred strategies for the clinic.
- Technical Assistance: On going, ad hoc technical support on the use and maintenance of the iPad (e.g., trouble launching the DA, problems navigating screens).
- Clinic Champion: - Designated member of clinic who is dedicated to supporting, marketing, and driving implementation of the DA in the clinic.
- Refresher Training Course: A webinar conducted every six months or as needed that describes the

implementation strategies, common barriers being confronted across the 16 participating clinics, and shares best practices of how these strategies are being deployed across the 16 clinics to sustain the intervention.

Tailored Implementation Activities

Sites will also have the option to choose from recommended Tailored Implementation Activities. These strategies are clinic-targeted and patient-targeted activities designed to stimulate participant recruitment and retention. Sites will choose either activity that is most relevant for implementation of the DA at their clinic and we anticipate that some sites will choose both activities. At the end of the study, all sites will be reviewed to determine with strategies were used throughout the duration of the study.

Clinic-targeted Activities:

- DA reminder in patient intake process
- Audit and feedback
- Team huddles/clinic meetings

Patient-targeted Activities

- Pre-visit web-based portal messages with
 - Access to decision aid via a link
 - Information regarding the study time demand
- Pre-visit delivery of paper-based version of decision aid
- Clinic poster about decision aid
- Decision-aid information through the waiting room TV/online kiosk

The DA will be given to all patient participants that meet the eligibility criteria during their regularly scheduled lupus clinic visit. Before reviewing the decision-aid, patients will view a short educational video on the purpose and use of the decision-aid. Questionnaires and the DA will be administered on an iPad, and questionnaires will take no more than 30 minutes on average, to keep responder burden low. Three and six-month follow-up questionnaires will be administered via phone, mail, or at the regularly scheduled clinic visit per the patient participant preference, and will last no more than 15 minutes.

In the event clinic personnel transition to a different position or leave the organization, they will be given a Clinic Personnel Exit interview* to assess the reason for departure, their view on the dissemination of the decision-aid into normal clinic flow, and the sustainability for future use.

Aim 2 Clinic Personnel Survey

Clinic personnel will complete a formative evaluation at 0-, 6-, 12- and 24- months of the study, receiving a survey to assess *acceptability, appropriateness, feasibility, success, and permanence of the DA*. This survey will be administered to up to 15 clinic personnel per site at most and will last for 10 minutes. Clinic personnel will receive an email with a link to complete the online Qualtrics survey. Reminder emails will be sent to non-responders 1- and 2-weeks after the initial survey email. All outcome will be measured on a Likert-type scale from (strongly agree = 1) to (strongly agree = 5). For composite outcomes, mean scale scores will be computed.

Specific Aim 3: Semi-structured interviews will be administered to the clinic personnel interviewed as part of Specific Aim 1, as well as 2 patient participants per site from Specific Aim 2, over the phone to reduce patient/clinic personnel burden. The interviews will be done by the UAB study team lead by [name], in collaboration with Drs. [name] and Qu, coordinated by [name] and [name]. These interviews will be conducted within 45-60 minutes and transcribed to

analyze the effectiveness of implementing the decision aid in a normal clinic setting and sustainability facilitators and barriers. These responses will develop the step-by-step implementation guide for future use in a clinic setting.

The study team will take into consideration the following while developing the interview guide for Specific Aim 3:

- Turnover in clinic personnel*
 - There may be turnover in clinic personnel whom were interviewed for Specific Aim 1. There will be specific questions in the interview guide for Specific Aim 2 to account for this.

Study coordinators will be interviewed every six months to assess the implementation and sustainability of the DA in the clinic flow. This survey will be given over the phone to one study coordinator per site every 6 months, lasting no more than 30 minutes per site. These interviews will be recorded and transcribed for study records; any actionable concerns will be decided upon in the following weekly study conference call.

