4 OBJECTIVES AND ENDPOINTS

Specific Aim 1: Conduct a formative evaluation and introduction to the DA in 16 diverse clinics to assess stakeholder needs and identify clinic and contextual characteristics (e.g., readiness for change, physician attitudes, patient barriers) to inform strategy component selection and influence implementation effectiveness of lupus DA (**Aim 2**). Penetration will be assessed by evaluating the proportion of eligible patients reviewing the DA overall and in each site. Patient healthcare utilization outcomes (e.g., inpatient visits and ER/urgent care visits) will be assessed similarly.

Specific Aim 2: Assess the effectiveness of a multi-component (standardized and tailored) strategy for the implementation of the DA in 16 lupus clinics (minimum 35 patients/clinic) by examining changes in subjective and objective measures of implementation effectiveness over 27 months. Objective measures will be assessed in both clinic personnel and in patients. Clinical personnel will evaluate perceived acceptability of intervention measure for the DA, perceived DA implementation success, and perceived DA permanence. All will be assessed on a Likert-type scale. Similarly, patients will evaluate perception of DA usefulness, patient satisfaction for the DA, perceived intervention appropriateness measure for the DA, and perceived feasibility of intervention measure for the DA. All of these patient assessments will be measured on a Likert-type scale.

Specific Aim 3: Identify opportunities for sustaining and disseminating the DA via semi-structured debriefing interviews with key clinic informants of Aims #1 and patients of Aim 2 and develop a manual that provides step-by-step implementation guide for incorporating the DA into regular lupus clinic visits and care pathways.

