9 STATISTICAL CONSIDERATIONS

9.1 STATISTICAL HYPOTHESES

Specific Aim 1: Targeted participants for this Specific Aim are key informants (interviews) and all clinic personnel (surveys). The purpose of this Specific Aim is to identify and quantify clinic and contextual characteristics (e.g., readiness for change, physician attitudes, patient barriers) to inform strategy component selection and influence implementation effectiveness of lupus DA to be evaluated in Specific Aim 2. As such the statistical approach for this component of Aim 1 is largely descriptive and there are no formal statistical null and alternative hypotheses. Specific descriptive statistics are described in the table below and further details are provided in Section 9.4. Penetration will be assessed by evaluating the proportion of eligible patients reviewing the DA overall and in each site. Overall rates and 95% confidence intervals will be computed. Patient healthcare utilization outcomes (e.g., inpatient visits and ER/urgent care visits) will be assessed similarly.

Specific Aim 1 Data Collection and Analyses		
Data Type	Data Collection Type	Analytic Methods
Quantitative	Online & paper survey, Organizational readiness for implementing change (ORIC); Team Learning & Psychological Safety Survey (TLPSS)/ Baseline	Individual & practice level summary statistics Correlation
Qualitative	Semi-structured interviews with key informants/ Baseline	Within-case/clinic thematic analysis of CFIR domains Cross-case/clinic comparison

Specific Aim 2: Targeted patient participants for this Specific Aim are (1) age \geq 18 years with a diagnosis of lupus from participating clinics; for individual-level outcomes, initial analyses will focus on how clinic personnel and patient perceptions change over time. The statistical null hypothesis is the assumption that there is no change over time versus

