the alternative that there is a change over time. For the analytic approach we will examine mean levels (total change) and quantify with means (or proportions, as appropriate) and 95% confidence intervals. We will also examine patterns of change (growth trajectories) while controlling for differences between clinics using multivariable models that account for repeated measures and clinic clustering of patients (i.e., generalized estimating equations (GEE) with robust standard errors). Additional analyses may examine by-group comparisons of clinics determined by clinical characteristics (e.g., geographic areas, clinic type, and patient diversity) observed in Specific Aim 1. Any such by-group analyses will be conducted separately. A primary independent variable of interest is the type of strategy used for implementation. Following completion of the study, each sites strategies will be evaluated and sites will be grouped accordingly. A covariate allowing for testing group differences will be included in the multivariable models to assess whether trajectories differ by implementation strategy.

The second component of our evaluation of Specific Aim 2 will use fuzzy set Qualitative Comparative Analysis (fsQCA) to assess effectiveness of implementation strategies for clinic-level outcomes. fsQCA is a case-oriented approach that examines relationships between conditions (similar to explanatory variables in regression models) and outcomes using set theory to answer the question: “what conditions, alone or in combination, are necessary or sufficient to produce an outcome?” For patient-physician communication analysis, question-asking, assertive responses, and expressions of concern, will be coded as patient participation; supportive talk and partnership building by provider will be coded as active physician communication. Further details are provided in Section 9.4.

Specific Aim 3: Targeted participants for this Specific Aim are the same key clinic informants from Specific Aim 1 and 2 patients per clinic from Specific Aim 2. Similar to Specific Aim 1, the analytic approach is largely descriptive and there are no formal statistical null and alternative hypotheses. Specific descriptive statistics are described in the table below. Further details are provided in Section 9.4.

Specific Aim 3 Data Collection and Analyses		
Data Type	Interview Content	Analytic Methods

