9.4.2 Analysis of the Primary Efficacy Endpoint(S)

Specific Aim 1:

Qualitative: Emergent theme analysis, within each clinic and based on the CFIR domains, will be initially conducted. These themes will be used to identify the preferred implementation strategies for use in a clinic. These within-case themes also will be used to compare and contrast between clinics to identify unique and common barriers to implementation.

Quantitative: Univariate statistics (means, standard deviations) will be used to describe each clinic's learning environment and readiness to implement change. Spearman correlations will be estimated to assess how different aspects of the clinic's learning environment and readiness to implement change may vary across clinics. Similarly, t-tests and one-way ANOVAs will be estimated to assess how the learning environment and readiness to change varies a

function of clinic characteristics (e.g., location, private vs. academic). Penetration will be assessed by evaluating the proportion of eligible patients reviewing the DA overall and in each site. Simple proportions and 95% confidence intervals will be computed. Patient healthcare utilization outcomes (e.g., inpatient visits and ER/urgent care visits) will be assessed similarly.

The results of the qualitative and quantitative analyses described above will be consolidated to construct a profile or “case study” for each clinic.

Specific Aim 2:

Targeted participants for this aim are (1) age \geq 18 years with a diagnosis of lupus from participating clinics. Objective measures will be assessed in both clinic personnel and in patients. Clinical personnel will evaluate perceived acceptability of intervention measure for the DA, perceived DA implementation success, and perceived DA permanence. All will be assessed on an ordinal scale (strongly disagree = 1) to (strongly agree = 5). Similarly, patients will evaluate perception of DA usefulness, patient satisfaction for the DA, perceived intervention appropriateness measure for the DA, and perceived feasibility of intervention measure for the DA. All of these patient assessments will be measured on a Likert-type scale.

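### Baseline readiness is said to inform strategy choice and influence implementation, but the model comparing strategies specifies no adjustment for it, leaving confounding of unknown direction and size

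*Combined protocol and SAP*

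**What the plan says.** All references are to the combined protocol and SAP.

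- **Role of readiness.** Section 4 (Aim 1), repeated in 9.1, describes a formative evaluation of clinic and contextual characteristics: "e.g., readiness for change, physician attitudes, patient barriers) to inform strategy component selection and influence implementation effectiveness of lupus DA". Readiness is thus tied to both the choice of strategy and the result of implementation.
- **Measurement.** The Aim 1 table in 9.1 lists "Organizational readiness for implementing change (ORIC); Team Learning & Psychological Safety Survey (TLPSS)/ Baseline" as the quantitative instruments, summarised at individual and practice level.
- **How strategies are chosen.** Under Training in 6.1, a webinar series one to two months after each site's formative evaluation "describes the clinic-specific findings of the formative evaluation, reviews the implementation strategies available to the clinic (both standardized and tailored", and then "jointly identifies the preferred strategies for the clinic". Section 6.1 also lets sites pick the tailored activities most relevant to them. Section 9.4.2 says of the interview themes: "These themes will be used to identify the preferred implementation strategies for use in a clinic".
- **The comparison.** Section 9.1 states: "A primary independent variable of interest is the type of strategy used for implementation". Sites are grouped after the study ends, and a group covariate enters the multivariable models to test whether trajectories differ by strategy. Section 9.4.7 envisages two groups.
- **Other adjustment.** Sections 9.1 and 9.4.2 say the GEE models control for differences between clinics but list no covariates. By-group analyses on Aim 1 characteristics are optional and run separately. Readiness is not in the subgroup list in 9.4.6.

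**The concern.** A characteristic measured before the choice, fed into the choice, and expected to affect the outcome is a confounder of the strategy comparison. The plan collects a score for it at baseline but uses that score only for description, correlations, t-tests or ANOVAs, and clinic profiles. If strategy groups differ in readiness, part of any difference between them may reflect the clinics rather than the strategies.

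What is at stake is the reading of a comparison that the plan itself calls primary. With 16 clinics, self-chosen strategies and groups formed at the end, chance balance on readiness cannot be relied on. Choosing adjustments after the groups are known would add a second problem.

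**Working it through.** **Inputs from the documents.** 16 clinics and ICC 0.05 (9.2); at least 35 patients per clinic (section 8); two strategy groups (9.4.7); significance level 0.05 (9.4.4), taken as two-sided.

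**Assumptions.** Equal split of 8 v 8; patient-level SD of 1; every association between readiness, strategy and outcome. The documents give none of these.

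**1. The plan's own figures.** No power or precision is stated for the strategy comparison. The nearest figures, in 9.2, are total 95% CI widths of 0.09 (SD 0.5) and 0.35 (SD 2.0) for one overall mean. They do not reproduce at the minimum enrolment:
- Design effect 1 + 34 × 0.05 = 2.7; effective n = 560/2.7 = 207.
- Widths 2 × 1.96 × 0.5/√207 = 0.14 and 2 × 1.96 × 2.0/√207 = 0.54.

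That is a separate matter. An interval for one overall mean is the wrong yardstick for a between-strategy contrast in any case.

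**2. Precision of the strategy contrast (levels).**
- SE = √[(0.05 + 0.95/35) × 2/8] = √(0.0771 × 0.25) = 0.139 SD.
- 95% half-width with 14 df = 2.145 × 0.139 = 0.30 SD.

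**3. Bias from omitting readiness (levels).** Let r be the correlation of readiness with the true clinic effect and d the readiness difference between strategy groups in SDs. Then bias = r × d × √0.05, with √0.05 = 0.224.
- r = 0.3, d = 0.5: 0.3 × 0.5 × 0.224 = 0.03 SD, or 0.034/0.298 = 11% of the half-width.
- r = 0.7, d = 1.0: 0.7 × 1.0 × 0.224 = 0.16 SD, or 0.157/0.298 = 53% of the half-width.

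**4. Simulation.** Clinic means with a true strategy effect of zero, 4,000 runs per setting, least squares on clinic means with a t test. Here r1 is the correlation of readiness with the latent choice of strategy, and r2 its correlation with the true clinic effect.

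| r1 | r2 | False effect, unadjusted (SD) | Type I error | Bias, adjusted (SD) | Type I error | SE, unadjusted to adjusted |
|---|---|---|---|---|---|---|
| 0 | 0.6 | 0.002 | 4.8% | -0.002 | 5.1% | 0.138 to 0.126 |
| 0.3 | 0.3 | 0.032 | 5.9% | 0.001 | 5.0% | 0.139 to 0.145 |
| 0.6 | 0.6 | 0.122 | 13.6% | 0.001 | 4.5% | 0.137 to 0.146 |
| 0.9 | 0.3 | 0.092 | 9.1% | -0.004 | 5.2% | 0.137 to 0.204 |
| 0.9 | 0.9 | 0.273 | 57.0% | -0.001 | 5.4% | 0.118 to 0.145 |

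The two approaches agree. The false effects at 0.3/0.3 and 0.6/0.6 correspond to d = 0.032/(0.3 × 0.224) = 0.48 and d = 0.122/(0.6 × 0.224) = 0.91. The last row is an extreme case, not an expectation. If readiness is unrelated to choice (r1 = 0), there is no bias.

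**5. Levels and trajectories.** These figures concern a difference in levels. Section 9.1 tests whether trajectories differ, which is strategy by time. The documents give no variance of change and no within-person correlation, so the bias in that contrast cannot be sized. A main effect of readiness alone would not adjust it.

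**The case against.** **The plan already controls for differences between clinics.** True as wording, so the supportable claim is that no readiness adjustment is specified, not that adjustment is ruled out. The wording does not supply it, however. Clinic fixed effects would be collinear with a clinic-level strategy main effect, and would leave strategy-by-time open to confounding by readiness-by-time.

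**Readiness does not decide the strategy.** A reader might infer from the webinar sequence that the readiness results determine the choice. The documents do not support that: findings inform a joint decision, interview themes are named as a driver in 9.4.2, and site preference counts under 6.1. This stands. It means that adjusting for readiness reduces confounding without necessarily removing it.

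**The direction is unknown.** A reader might infer that readier clinics will make their strategy look successful. Nothing in the plan shows which clinics take which activities. Less ready clinics may take more support, which would reverse the bias. Section 6.3 expects 16 different approaches, and 9.4.7 allows the groups to be redefined. This also stands.

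**The bias may be small.** With correlations of 0.3 the type I error is 5.9%, which hardly matters.

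**Other parts of the plan help.** The fuzzy-set analysis is a separate component whose conditions are not listed, so readiness is neither included nor excluded there, and it does not adjust the GEE contrast. The bias statements in 5.1 and 6.2 concern which clinics were recruited. Calling the design observational is fair, but 9.1 still tests strategy differences formally.

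**Adjustment can be costly.** Correct where readiness strongly drives choice: the standard error reached 0.204 SD in one setting. ORIC also comes from at most 15 staff per clinic, so it is measured with error.

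**Conclusion.** The point holds. The plan names readiness as informing strategy selection and influencing effectiveness, measures it at baseline, and specifies no adjustment for it in a comparison it treats as primary. The strategy contrast is therefore open to confounding of unknown direction and size.

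Under assumed readiness-outcome correlations of 0.3 to 0.7 and group differences of 0.5 to 1.0 SD, the false difference in levels is about 0.03 to 0.16 SD. That is roughly a tenth to a half of the 0.30 SD half-width. It is therefore not correct to infer that the bias would swamp the comparison. It could still distort the estimate and, at moderate correlations, raise the type I error to about 14%. All of this assumes an 8 v 8 split, 35 patients per clinic and ICC 0.05. No figure can be given for trajectories.

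**What to change.** In 9.1 and 9.4.2:

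1. Prespecify the clinic-mean baseline ORIC score as a covariate in the GEE containing strategy, with ORIC-by-time wherever strategy-by-time is tested.
2. Report the strategy estimate with and without ORIC.
3. Repeat with TLPSS in place of ORIC as a sensitivity analysis.
4. Describe the strategy result as an association, stating that interview themes and site preference also drive the choice and that residual confounding remains.

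Cost: SAP wording only, since both scores are already planned at baseline. Clinic-level residual degrees of freedom fall from 14 to 13 for the contrast in levels. The standard error widens if readiness and strategy are correlated: 0.137 to 0.146 SD at moderate correlation (0.6/0.6), and up to about 0.20 SD at very high correlation with choice (0.9/0.3). Where readiness predicts the outcome well but is unrelated to choice, adjustment narrows it (0.138 to 0.126 SD at 0/0.6). Showing both estimates makes this trade-off visible.
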